5.5 RANDOMISATION

5.5.1 Randomisation

Randomisation will be to left or right side within each individual as we cannot consider pain experiences on right vs. left within an individual as being independent. We want to compare pain immediately after PDT illumination (time-point of most interest) and, as another way of comparing between the interventions "pain experience over-time" (while trying to reduce the multiple comparisons "problem"), to compare within-subjects Areas Under the Curve of pain over time.

Patients will be randomly allocated to either active or placebo treatment to right or left side using a computer-generated block randomisation sequence, which will also include randomisation as to which side will be treated first. The randomisation code will be generated by Tayside Pharmaceuticals and will be concealed from study investigators.

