9 STATISTICS AND DATA ANALYSIS

9.1 SAMPLE SIZE CALCULATION

We were not able to obtain variance for within-subjects pain differences from similar studies. An assessment of pain experience with PDT in our unit found a standard deviation of between subjects VAS pain score of 2.7cm. Rounding this up to 3cm and conservatively estimating that within-subject's pain score SD will be two-thirds of this (2cm) then we estimated that 21 subjects should give us 90% power to detect a mean difference in VAS scores of 1.5 cm as significant at the 5% level. To allow for dropouts, assuming dropout rate by 3 months of up to 30%, we will recruit 30 subjects.

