9.2 PROPOSED ANALYSES

The main analysis will be the difference between within-subject pain using appropriate paired methods (paired Student's t-test if assumptions met). The difference will be expressed with 95% confidence interval. VAS scores immediately after PDT and the areas under the curve for pain scores plotted over each of the time points will be assessed. Within subject comparisons of fluorescence, phototoxicity, efficacy and patient evaluation will be secondary outcome measures, using paired statistical analyses.

Amendment

Since the original concept and set up of the study, there have been changes in the practice of PDT for AKs on the face and scalp, with low illuminance daylight PDT now favoured when practicable because this form of PDT is less painful than conventional PDT. Therefore, we will perform (statistical analysis by someone not involved in patient treatments and assessments, to ensure blinding) an interim analysis. With the same assumptions as before with a power of 90% we expect to detect a difference (at alpha = 0.1 level, two tailed testing) of 3 cm or more (on VAS) in pain between groups with 9 subjects should such a difference exist. We will therefore recruit a minimum of 9 participants and if on this interim analysis such a difference is detected then the study will be continued as originally planned in order to determine whether the difference can be detected at alpha = 0.05 level of significance, unless the dermatologist analysing the data advises stopping early as a greater difference already detected. If it seems unlikely that there will be a difference of ≥ 3 cm in pain

A randomised double blind, placebo controlled study of the efficacy of topical menthol for pain relief during topical photodynamic therapy

v.6.0 27/March/2019

on VAS based on this interim analysis, then (with the changes in use of PDT for AKs on face and scalp) the data analyst will advise stopping the study.

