14.4 END OF STUDY

The end of study is defined as last patient last visit (LPLV). The Sponsor and CI have the right at any time to terminate the study for clinical or administrative reasons. The end of the study will be reported to the Sponsor, REC, Regulatory Authority and NHS R&D Office within 90 days, or 15 days if the study is terminated prematurely. The CI will ensure that any appropriate follow up is arranged for all participants. A final report of the study will be provided to the Sponsor, REC and Regulatory Authority within 1 year of the end of the study.

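### Section 9.2 allows advice to stop early for benefit with no numeric boundary and keeps the final test at 0.05, so the 5% error rate depends on how the clause is read

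*Combined protocol and SAP*

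**What the plan says.** Section 9.1 plans 21 completers (30 recruited) for 90% power to detect a mean difference of 1.5 cm at the 5% level. The amendment in section 9.2 inserts one interim analysis after at least 9 participants, planned to detect a difference "at alpha = 0.1 level, two tailed testing) of 3 cm or more (on VAS"). If that difference is found, the trial continues to the planned size "in order to determine whether the difference can be detected at alpha = 0.05 level of significance". One exception follows directly: "unless the dermatologist analysing the data advises stopping early as a greater difference already detected". If a 3 cm difference looks unlikely, the analyst advises stopping; no number defines unlikely.

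The interim is to be run by someone independent of patient care ("statistical analysis by someone not involved in patient treatments and assessments, to ensure blinding"). The analyst only advises. Under section 14.4, "The Sponsor and CI have the right at any time to terminate the study for clinical or administrative reasons". That general right supplies no statistical boundary, and nothing else in the documents does.

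**The concern.** A look that can end the trial with a claim of benefit uses up part of the type I error. A plan normally states the boundary for that look and sets the final level so that the two together total 5%. Here the boundary is unstated and the final test keeps the full 0.05.

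Two meanings fit the sentence:

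- **(a) Size.** The observed difference exceeds the 3 cm named just before.
- **(b) Significance.** The difference is already significant at 0.05. The clause directly follows the mention of that level, and sections 9.1 and 9.2 tie the word detect to a significance level.

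Two analysts could act differently on the same result. If the trial stopped early, no one could say whether the rule had been followed, and a boundary chosen after the data are seen cannot repair this.

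**Working it through.** **Inputs.** From 9.1: SD 2 cm, effect 1.5 cm, 21 completers, level 5% (taken as two-sided). From 9.2: interim at 9, paired t-test, final level 0.05. The benefit boundary is not given.

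**The plan's own figure.** For a paired t-test with n=21 and SD of differences 2 cm, the noncentrality is 1.5/(2/√21) = 3.44 on 20 df. Power is 90.5%, so the stated 21 is reproduced with 2 cm as the SD of the *difference*.

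**Range for the SD.** Section 9.1 derives the 2 cm from a survey that "found a standard deviation of between subjects VAS pain score of 2.7cm", and could also be read as giving the SD of a single score. The interim figure of 9 points that way: two independent groups with SD 2 cm per side, 3 cm and 0.10 two-sided give 91.9% power at 9 per group and 88.6% at 8. On that reading the SD of the difference is 2×√2 = 2.83 cm. With a between-subject SD of 2.7 cm, the left-right correlation is 1 − SD²/(2×2.7²), which is 0.73 at 2 cm and 0.45 at 2.83 cm. Both agree with section 5.5.1, where "we cannot consider pain experiences on right vs. left within an individual as being independent".

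**How far apart the readings are.** At n=9, p<0.05 needs an observed mean of t(0.975, 8 df)×SD/√9 = 2.306×SD/3. That is 1.54 cm at SD 2 cm and 2.17 cm at SD 2.83 cm, both well below 3 cm.

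**Reading (a) under the null.** The standard error at n=9 is 2/3 = 0.667 cm, so 3 cm is 4.5 standard errors (two-sided chance about 0.000007). At SD 2.83 cm it is 0.943 cm, so 3 cm is 3.18 standard errors (chance about 0.0015). The overall error therefore cannot exceed 0.05 + 0.0015 = 0.0515.

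**Reading (b) under the null.** Each look rejects 5% of the time. Simulation puts both rejecting at about 1.3%, so the overall error is 5 + 5 − 1.3 = 8.7%.

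**Overall two-sided type I error** (simulated paired t-tests at 9 and 21, final level 0.05, early stop counted as a positive claim):

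| Meaning of the clause | Futility advice not followed | Continue only if interim p<0.10 (assumed proxy) |
|---|---|---|
| No stop for benefit | 5.0% | 2.1% |
| Observed above 3 cm, with or without p<0.05, SD 2 cm | 5.0% | 2.1% |
| The same, SD 2.83 cm | 5.1% | 2.2% |
| Interim p<0.05, any size | 8.7% | 5.8% |

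With 30 analysed, the last row is 9.0% and 5.6%.

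**Estimate after an early stop.** This applies only to reading (b) with no size condition. A true 1.5 cm at SD 2 cm would stop the trial at 9 participants in 51% of cases, with a mean estimate of 1.96 cm (1.96/1.5 = 1.31, so 31% too high). At SD 2.83 cm the figures are 29% and about 2.5 cm.

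**The case against.** The strongest reply is that reading (b) is strained. The exception sits inside a sentence that begins with detection of 3 cm or more, and a *greater* difference most naturally compares sizes. If an observed 3 cm is required as well as p<0.05, the error returns to 5.0 to 5.1%, and a true 1.5 cm would stop early in only about 1.2% of cases at SD 2 cm (about 5.5% at 2.83 cm). If reading (b) is combined with continuing only on an observed 3 cm or more, the error is also 5.0%. This stands: the most literal reading is nearly harmless. But the plan does not commit to it.

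Two further replies stand in part. If only stops favouring menthol count, reading (b) gives 6.9% rather than 8.7%, which is still above 5%. Also, section 9.2 calls for a 95% confidence interval, so a reader could recover the interim p-value. That allows the result to be judged against some boundary, but not against one fixed beforehand.

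Stronger conclusions that a reader might infer are not supported:

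- *The trial runs at 8.7%.* That holds only on reading (b) with the futility advice not followed.
- *Interim p<0.10 is enough to stop for benefit.* This would give 12.9%, but in section 9.2 detection at 0.10 is the condition for continuing.
- *The dermatologist alone can end the trial.* The text gives a power to advise; termination rests with the Sponsor and CI.

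**Conclusion.** The point holds as a missing pre-specified boundary with conditional inflation. The plan as written does not secure its 5% level: about 5.0 to 5.1% if *greater* means an observed difference above 3 cm, and about 8.7% if it means only interim p<0.05, or 5.8% under the assumed p<0.10 continuation rule. Because the futility rule is advisory and unquantified, the figures with that advice not followed are the prudent ones to quote. An actual excess is not shown.

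The figures assume normally distributed paired differences, exactly 9 evaluable participants at the interim, 21 at the end, and an SD of differences of 2 to 2.83 cm. The clause should be settled before the interim data are seen.

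**What to change.** Choose one.

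1. **Delete the exception**, from *unless* to *already detected*. The interim then serves futility only, and the final test stays at 0.05.
2. **State one strict boundary.** For example: stop for benefit only if two-sided p<0.001 on the immediate VAS at 9 evaluable participants. Section 5.5.1 supports that endpoint: "pain immediately after PDT illumination (time-point of most interest"). A final level of 0.0494 with 21 analysed (0.0493 with 30) gives an overall 5.0%. Leaving the final level at 0.05 gives about 5.05%, so the adjustment is a refinement; the stated boundary is what matters. The value 0.001 is one reasonable choice among several.

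A threshold in cm would also remove the ambiguity, but its error rate moves with the SD. For 3 cm it rises to 5.4% at an SD of 3.31 cm (2.7×√(2×0.75), assuming a left-right correlation of 0.25).

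**Cost.** This is a wording change with no extra participants. Early stopping for benefit becomes impossible under (1) and rare under (2) unless the effect is large. At SD 2 cm the chance under (2) is about 41% for a true 3 cm and 4.5% for a true 1.5 cm; at 2.83 cm it is 14% and 1.6%. Power for 1.5 cm at SD 2 cm stays at about 90% with or without the change, when the futility advice is not followed.

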10 ADVERSE EVENTS

10.1 DEFINITIONS

An **adverse event** (AE) is any untoward medical event affecting a clinical trial participant. Each initial AE will be considered for severity, causality or expectedness and may be reclassified as a serious event or reaction based on prevailing circumstances.

An **adverse reaction** (AR) is where it is suspected that an AE has been caused by a reaction to a trial drug

A **serious adverse event** (SAE), **serious adverse reaction** (SAR) or **suspected unexpected serious adverse reaction** (SUSAR) is any AE, AR or UAR that at any dose:

- results in death
- is life threatening
- requires hospitalisation or prolongation of existing hospitalisation
- results in persistent or significant disability or incapacity
- is a congenital anomaly or birth defect
- Or is otherwise considered serious

Note: Hospitalisations for treatment planned prior to randomisation and hospitalisation for elective treatment of a pre-existing condition will not be considered as an SAE. However any adverse events occurring during such hospitalisation will be recorded.

10.2 RECORDING AND REPORTING AES AND SAES

Topical menthol may cause a sensation of cooling and hyperalgesia and, with repeated applications may cause some skin irritation. However, with a single 10 minute application to a small area, as proposed in this study, we do not anticipate any adverse effects and, indeed, any cooling, hyperalgesic effect may be desirable with respect to potential pain relief. The clinical data and Reference Safety Information (RSI) are summarised in **Appendix 2**.

All AEs and SAEs will be recorded from the time a participant consents to join the study until the last study visit. Participants with unresolved AEs at the last study visit will be followed up until resolution or 30 days after last patient, last visit (LPLV), whichever is sooner. SUSARS will be followed until resolution.

The CI or delegate will ask about the occurrence of AEs and hospitalisations at every visit during the study. AEs will be recorded on the AE Log in the CRF. SAEs will be submitted on an SAE form to the TASC Safety Section ([contact]) within 24 hours of becoming aware of the SAE. SAEs will be assessed for expectedness and causality by the Investigator. The evaluation of expectedness will be made based on the knowledge of the reaction and

A randomised double blind, placebo controlled study of the efficacy of topical menthol for pain relief during topical photodynamic therapy

v.6.0 27/March/2019

the relevant product information (**simplified IB; Appendix 2**). Refer to TASC SOP 11 "Identifying, Recording and Reporting Adverse Events for CTIMPs".

10.3 REGULATORY REPORTING REQUIREMENTS

The Sponsor, together with the CI, is responsible for reporting SUSARs to the competent authority, the MHRA, the Research Ethics Committee (REC) and any other competent authorities. Fatal or life threatening SUSARs will be reported within 7 days and non-fatal and non-life threatening SUSARs within 15 days.

10.4 ANNUAL REPORTING REQUIREMENTS

The following reports will be submitted each year as a condition of the authorisation to undertake a clinical trial or as a condition of a favourable opinion from a REC.

The Development Safety Update Report (DSUR) will be prepared jointly by the TASC Safety Section and CI and submitted to the MHRA on the anniversary of date of Clinical Trial Authorisation (CTA).

An NRES CTIMP Safety Report Form will be sent to REC along with the DSUR. Reports of SUSARs in the UK, urgent safety measures and any other safety reports submitted, for example, reports of a data monitoring committee, will also be accompanied by a Safety Report Form.

A NRES Annual Progress Report for CTIMPs will be prepared and submitted by the CI to REC, and copied to Sponsor, on the anniversary date of the REC favourable opinion.

10.5 URGENT SAFETY MEASURES

The CI or other clinician may take appropriate immediate urgent safety measures in order to protect the participants of a CTIMP against any immediate hazard to their health or safety. The MHRA, REC and Sponsor will be notified in writing within three days.

11 PREGNANCY

Pregnancy is not considered an AE or SAE, unless there is a congenital abnormality or birth defect. Any unexpected pregnancy occurring during the clinical study and the outcome of the pregnancy, will be recorded on a TASC Pregnancy Notification Form and submitted to the TASC Safety Section ([contact]) within 24 hours of becoming aware of the pregnancy. The pregnancy will be followed up until the end of the pregnancy. If the study participant is a male, informed consent for follow up must be sought and obtained from his female partner. This study will only be undertaken in women who are >50 years old and post-menopausal.

A randomised double blind, placebo controlled study of the efficacy of topical menthol for pain relief during topical photodynamic therapy

v.6.0 27/March/2019

12 TRIAL MANAGEMENT AND OVERSIGHT ARRANGEMENTS

12.1 TRIAL MANAGEMENT GROUP

The trial will be co-ordinated by a Trial Management Group, consisting of the CI, Trial Technologist and research nurse who will meet on a weekly basis. The TMG will also be responsible for oversight of data monitoring.

12.2 TRIAL MANAGEMENT

A Research Nurse will oversee the study and will be accountable to the CI. The Research Nurse will be responsible for checking the CRFs for completeness, plausibility and consistency. However, this will remain the overall responsibility of the CI. Any queries will be resolved by the CI or delegated member of the trial team.

A study-specific Delegation of Responsibilities & Signature Log will be prepared, detailing the responsibilities of each member of staff working on the trial.

12.3 INSPECTION OF RECORDS

The CI and the institutions involved in the study will permit trial related monitoring, audits, REC review, and regulatory inspection(s). In the event of an audit, the CI will allow the Sponsor, representatives of the Sponsor or regulatory authorities direct access to all study records and source documentation.

12.4 RISK ASSESSMENT

A study risk assessment was carried out by the TASC Research Governance Manager prior to Sponsorship approval being granted.

12.5 STUDY MONITORING

The Sponsor has determined the appropriate extent and nature of monitoring for the trial and will appoint appropriately qualified and trained monitors. Thus, any potential risks will be minimized,

13 GOOD CLINICAL PRACTICE

13.1 ETHICAL CONDUCT OF THE STUDY

The study will be conducted in accordance with the principles of good clinical practice (GCP). In addition to Sponsorship approval, a favorable ethical opinion will be obtained from an appropriate REC. Authorisation from an appropriate competent authority(s) and appropriate NHS R&D permissions(s) will be obtained prior to commencement of the study.

13.1.1 Confidentiality

All laboratory specimens, evaluation forms, reports, and other records will be identified in a manner designed to maintain participant confidentiality. All records will be kept in a secure storage area with limited access to study staff only. Clinical information will not be released without the written permission of the participant, except as necessary for monitoring and auditing by the Sponsor, its designee or Regulatory Authorities. The CI and study staff involved with this study will not disclose or use for any purpose other than performance of the study, any data, record, or other unpublished, confidential information disclosed to those individuals

A randomised double blind, placebo controlled study of the efficacy of topical menthol for pain relief during topical photodynamic therapy

v.6.0 27/March/2019

for the purpose of the study. Prior written agreement from the Sponsor or its designee will be obtained for the disclosure of any said confidential information to other parties.

13.1.2 Data Protection

The CI and study staff involved with this study will comply with the requirements of the Data Protection Act 1998 with regard to the collection, storage, processing and disclosure of personal information and will uphold the Act's core principles. The CI and study staff will also adhere, if appropriate, to the current version of the NHS Scotland Code of Practice on Protecting Patient Confidentiality. Access to collated participant data will be restricted to the CI and appropriate study staff.

Computers used to collate the data will have limited access measures via user names and passwords.

Published results will not contain any personal data that could allow identification of individual participants.

13.1.3 Insurance and Indemnity

The University of Dundee and Tayside Health Board are Co-Sponsoring the study.

Insurance. – The University of Dundee will obtain and hold Professional Negligence Clinical Trials Insurance cover for legal liabilities arising from the study.

Tayside Health Board will maintain its membership of the Clinical Negligence and Other Risks Insurance Scheme (“CNORIS”) which covers the legal liability of Tayside in relation to the study].

Where the study involves University of Dundee staff undertaking clinical research on NHS patients, such staff will hold honorary contracts with Tayside Health Board meaning they will have cover under Tayside's membership of the CNORIS scheme.

Indemnity. The Co-Sponsors do not provide study participants with indemnity in relation to participation in the Study but have insurance for legal liability as described above.

14 STUDY CONDUCT RESPONSIBILITIES

14.1 PROTOCOL AMENDMENTS

The CI will seek Sponsor approval for any amendments to the Protocol or other study documents. Amendments to the protocol or other study docs will not be implemented without approval from the Sponsor and subsequent approval from the appropriate REC and/or Regulatory Authority, as appropriate, and NHS R&D Office. Refer to TASC SOP 26 “Amendments to CTIMPs”

14.2 PROTOCOL DEVIATIONS, BREACHES AND WAIVERS

The CI will not implement any deviation from the protocol without agreement from the Sponsor, except where necessary to eliminate immediate hazard to trial participants.

In the event that the CI needs to deviate from the protocol, the nature of and reasons for the deviation will be recorded in the CRF, documented in a TASC Deviation & Breach Log and notified to the Sponsor. If this necessitates a subsequent protocol amendment, this will be submitted to the Sponsor for approval and then to the appropriate REC, Regulatory Authority and local NHS R&D for review and approvals as appropriate. It is Sponsor policy that waivers to the Protocol will not be approved.

A randomised double blind, placebo controlled study of the efficacy of topical menthol for pain relief during topical photodynamic therapy

v.6.0 27/March/2019

In the event that a serious breach of the protocol or GCP is suspected, this will be reported to the Sponsor immediately using the form “Notification to Sponsor of Potential Serious Breach or Serious Deviation”. Refer to TASC SOP 25 “Escalation and Notification of Serious Breaches of GCP or the Trial Protocol for CTIMPs”.

14.3 STUDY RECORD RETENTION

Archiving of study documents will be carried out as specified in TASC SOP 13: Archiving Clinical Research Data for Clinical Trials of Investigational Medicinal Products. For studies where the data does not form part of an application for a Marketing Authorisation (MA) all study documentation will be kept for at least 5 years. For studies where the data does form part of an application for a Marketing Authorisation (MA) all study documentation will be kept for at least 15 years.

